### 9.6 Visit 6 (Day 85 ± 3): Week 12/End of Treatment

**One day prior to the visit, the site staff will contact the subject to remind them to note the time of dosing in the Subject Instruction Sheet if the subject chooses to take the morning dose of test article on the day of their clinic visit at home and to inform them**

**that if the subject chooses to take the morning dose of test article in the clinic, the subject will need to remain in the clinic for 1 hour after dosing.**

*At this visit, the investigator or designee will:*

- Query the subject for any changes in health status since the previous visit, including concomitant medications and concurrent procedures/therapies, and document the findings.
- Measure vital signs (see Section 10.7.1).
- Have the subject perform the subject evaluation (PGIC). See Section 10.6.
- Perform clinical evaluations (IGA first, then BSA and PASI). See Section 10.3, Section 10.5, and Section 10.4, respectively.
- Perform a targeted physical exam (see Section 10.7.2). Record any new or worsening clinically significant abnormalities as AEs.
- Perform ECG (see Section 10.7.3).
- From the same areas collected at baseline, collect non-invasive skin samples from lesional and non-lesional (perilesional to the lesional sample) skin (see Section 12.2).
- Document Test Article Accountability; all test articles will be collected and tablets will be counted.
- If the subject chose to take the test article in the clinic, administer the morning dose of test article to the subject.
- Record dosing time. Note: dosing time can be obtained verbally from the subject, from the Subject Instruction Sheet, or from administration in the clinic.
- Collect blood for blood biomarker analysis (RASP ELISAs and cytokines) **no earlier than 1 hour after** test article administration (see Section 12.3).
- Collect blood and urine samples for clinical laboratory tests (chemistry, hematology, and urinalysis). If possible, subjects should be fasting for approximately 8 hours.
- Perform a UPT for all WOCBP.
- Document any AEs.
- Schedule the subject for a phone call follow-up visit 3 days after this visit.

## **9.7 Visit 7 (3 days after Visit 6): End of Study**

*During this phone call, the investigator or designee will:*

- Query the subject for any changes in health status since the previous visit including concomitant medications and concurrent procedures/therapies, and document the findings.
- Document any AEs.
- In the event that 3 days after Visit 6 occurs on a weekend, the site may call the subject on the Monday to follow as/if necessary.
- Exit the subject from the study.

## 10. CLINICAL EVALUATIONS

The following clinical evaluations will be performed according to the Schedule of Events. The same expert grader who has received training on how to properly perform the IGA and PASI clinical evaluations should ideally complete the evaluations for a given subject throughout the trial. If this is not possible (e.g., scheduling conflict), a different expert grader with overlapping experience with the subject and the trial should complete the evaluations.

### 10.1 Skin Biomarker Analysis

Skin tape strips will be collected from all participants for whole RNA transcript analysis, respectively. The purpose of these analyses will be to retrospectively evaluate biomarkers predictive of subject response at baseline, prior to test article administration, as well as to potentially identify additional correlative and pharmacodynamic biomarkers [5].

### 10.2 Blood Biomarker Analysis

Plasma will be collected, stored at -70°C, and sent under frozen conditions to Charles River Laboratories (Senneville, Quebec, Canada) for RASP ELISA and cytokine assays.

Sera and Plasma will be further analyzed for changes from baseline in circulating inflammatory mediators.

### 10.3 Investigator's Global Assessment

The IGA score is a static evaluation of the overall severity or “average” degree of severity of a subject’s disease, taking into account all of the subject’s psoriatic lesions (excluding those on the face, scalp, groin, axillae, and other intertriginous areas) by the investigator or designee as the subject appears on the day of the evaluation. The evaluation takes into consideration the 3 individual characteristics of psoriasis (plaque elevation, scaling, and erythema) with the IGA score at each visit representing the average degree of plaque elevation, scaling, and erythema that is present amongst all of the lesions.

**The investigator should NOT refer to any other assessments to assist with this evaluation.** This evaluation is NOT a comparison with the IGA at any other visit or a mathematical calculation based on the clinical signs of psoriasis scores. At every trial visit, the investigator or designee will evaluate all active psoriasis plaques in the subject’s entire body) and report the one whole integer score that describes the average IGA using the following scale:

CLEAR (0)	
Plaque elevation	No evidence of plaque elevation above normal skin level.
Scaling	No evidence of scaling.
Erythema	No erythema (hyperpigmentation may be present).

ALMOST CLEAR (1)	
Plaque elevation	No more than a very slight elevation above normal skin level, easier felt than seen.
Scaling	No more than limited amount of very fine scales partially covers some of the plaques.
Erythema	No more than faint red coloration.

MILD (2)	
Plaque Elevation	No more than a slight but definite elevation above normal skin level, typically with edges that are indistinct or sloped, on some of the plaques.
Scaling	No more than mainly fine scales; some plaques are partially covered.
Erythema	No more than light red coloration.

MODERATE (3)	
Plaque Elevation	No more than a moderate elevation with rounded or sloped edges on most of the plaques.
Scaling	No more than somewhat coarser scales predominate; most plaques are partially covered.
Erythema	No more than moderate red coloration.

SEVERE (4)	
Plaque elevation	Marked elevation with hard sharp edges on virtually all of the plaques.
Scaling	Coarse, thick tenacious scales predominate; virtually all or all plaques are covered; rough surface.
Erythema	Dusky to deep red coloration.

#### 10.4 Psoriasis Area and Severity Index

The severity of plaque psoriasis by body region (head, upper limbs, trunk, and lower limbs) and the percentage area affected by body region will be assessed. For each body region, erythema, induration/thickness, and scaling will be graded using a 5-point scale (0=clear, 1=slight (mild), 2=moderate, 3=severe, 4=very severe) and the percent involvement of each body region will be assigned a numeric score (from the BSA assessment described below): 0% (0), 1% – 9% (1), 10% – 29% (2), 30% – 49% (3), 50% – 69% (4), 70% – 89% (5) or 90% – 100% (6). The sign scores for each body region will be summed and multiplied by

the Area Score, and then multiplied by the amount of body surface area assigned to that body region (0.1 for head, 0.2 for upper limbs, 0.3 for trunk, and 0.4 for lower limbs). The sum of PASI scores by body region will give the total PASI score, which may range from zero (0) to a maximum of 72. See Appendix 3.

#### **10.5 Body Surface Area**

Calculation of the PASI score requires an area score in 4 anatomic regions of the body (head; upper limbs; trunk; and lower limbs). To calculate the total BSA, the Investigator or designee will determine the absolute percent BSA of psoriasis involved skin disease in each of the 4 anatomic regions. Then, the total BSA will be calculated as the sum of the values in each of the 4 anatomic regions. BSA in each anatomic region will be determined using the hand method, whereby the subject's hand surface area (palm with fingers held in juxtaposition to each other) represents about 1% of the subject's BSA. All assessments will be recorded in the eCRF. This BSA assessment in each region shall include 1 decimal point of precision (e.g., 11.0, 1.3). The amount of BSA involved in each of the 4 anatomic regions will (i) be used to assign the Area Score in the calculation of the PASI score and (ii) be summed to provide a Total BSA for the subject (at Visit 1/Screening and Visit 2/Baseline). The assignment of these values (i.e., Area Scores for the PASI assessment and Total BSA) will be "determined" by the electronic data capture (EDC) software based upon the Investigator's (or designee) assignment of the absolute percent BSA of diseased psoriasis skin within each of the 4 anatomic regions of the body (head; upper limbs; trunk; and lower limbs).

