Trial Measurements	
Safety: Vital signs, physical examinations, 12-lead ECGs, clinical laboratory tests, UPTs, and AEs will be recorded per the schedule of events.
 
Metabolite Profiling: Urine and plasma drug metabolite analysis will take place according to the schedule of events.
 
Clinical and Biomarker: Skin Biomarker Analysis Skin tape strips will be collected from all participants for whole RNA transcript analysis. The purpose of these analyses will be to retrospectively evaluate biomarkers predictive of subject response at baseline, prior to test article administration, as well as to potentially identify additional correlative and pharmacodynamic biomarkers.

Sera and plasma will be further analyzed for changes from baseline in circulating inflammatory mediators.

*Psoriasis Area and Severity Index*

The severity of plaque psoriasis by body region (head, upper limbs, trunk, and lower limbs) and the percentage area affected by body region will be assessed. For each body region, erythema, induration/thickness, and scaling will be graded using a 5-point scale (0=clear, 1=slight (mild), 2=moderate, 3=severe, 4=very severe) and the percent involvement of each body region will be assigned a numeric score (from the BSA assessment described below): 0% (0), 1% – 9% (1), 10% – 29% (2), 30% – 49% (3), 50% – 69% (4), 70% – 89% (5) or 90% – 100% (6). The sign scores for each body region will be summed and multiplied by the Area Score, and then multiplied by the amount of body surface area assigned to that body region (0.1 for head, 0.2 for upper limbs, 0.3 for trunk, and 0.4 for lower limbs). The sum of PASI scores by body region will give the total PASI score, which may range from zero (0) to a maximum of 72.

*Investigator's Global Assessment*

The IGA is a single item measure that assesses the investigator's impression of overall severity of the subject's plaque psoriasis. The evaluation takes into consideration the 3 individual characteristics of psoriasis (plaque elevation, scaling, and erythema) with the IGA score at each visit representing the average degree of plaque elevation, scaling, and erythema that is present amongst all of the lesions using a 5-point visual rating scale ranging from 0 (clear) to 4 (severe).

*Body Surface Area*

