Calculation of the PASI score requires an area score in 4 anatomic regions of the body (head; upper limbs; trunk; and lower limbs). To calculate the total BSA, the Investigator or designee will determine the absolute percent BSA of psoriasis involved skin disease in each of the 4 anatomic regions. Then, the total BSA will be calculated as the sum of the values in each of the 4 anatomic regions. BSA in each anatomic region will be determined using the hand method, whereby the subject's hand surface area (palm with fingers held in juxtaposition to each other) represents about 1% of the subject's BSA. All assessments will be recorded in the electronic case report form (eCRF). This BSA assessment in each region shall include 1 decimal point of precision (e.g., 11.0, 1.3). The amount of BSA involved in each of the 4 anatomic regions will (i) be used to assign the Area Score in the calculation of the PASI score and (ii) be summed to provide a Total BSA for the subject (at Visit 1/Screening and Visit 2/Baseline). The assignment of these values (i.e., Area Scores for the PASI assessment and Total BSA) will be "determined" by the electronic data capture (EDC) software based upon the Investigator's (or designee) assignment of the absolute percent BSA of

	
diseased psoriasis skin within each of the 4 anatomic regions of the body (head; upper limbs; trunk; and lower limbs).
 
Patient Global Impression of Change
 
The PGIC is a single item measure that assesses the subject's impression of overall change from Baseline of plaque psoriasis signs and symptoms at the time the questionnaire is administered, using a 7-point visual rating scale ranging from 1 (much improved) to 7 (much worse).

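### Does Protocol 10.5 score the PASI area bands on whole-body percentages instead of percentages of each region?

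*Protocol*

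**What the plan says.** **What is recorded.** In Protocol 10.5 and the synopsis, "the Investigator or designee will determine the absolute percent BSA of psoriasis involved skin disease in each of the 4 anatomic regions". The unit is the subject's hand ("palm with fingers held in juxtaposition to each other) represents about 1% of the" subject's body surface), and the four values are added to give total BSA. They are therefore percentages of the whole body. On precision, 10.5 says: "This BSA assessment in each region shall include 1 decimal point of precision".

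**What is done with it.** Protocol 10.5 says: "The amount of BSA involved in each of the 4 anatomic regions will (i) be used to assign the Area Score". It leaves the step to the EDC software, which works from the investigator's "assignment of the absolute percent BSA of diseased psoriasis skin within each of the 4 anatomic regions of the body".

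**What is scored.** In Protocol 10.4, the synopsis and SAP 6.1, "the percent involvement of each body region will be assigned a numeric score (from the BSA assessment described below"), with bands running from 0% (score 0) to 90–100% (score 6). The sum of the three sign grades is multiplied by the Area Score and by the region's share of body surface: "0.1 for head, 0.2 for upper limbs, 0.3 for trunk, and 0.4 for lower limbs". Section 10.4 closes with the range of the total, "which may range from zero (0) to a maximum of 72. See Appendix 3".

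**Where it is used.** PASI of at least 12, together with BSA of at least 8%, is an entry criterion (Protocol 5.1.1). Change in PASI is the SAP's primary clinical efficacy endpoint (SAP 8.7.1), and PASI-50 and PASI-75 derive from it.

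**The concern.** Two adjacent sections use different scales. Section 10.5 names a whole-body percentage as the input to the Area Score, and 10.4 bands a percentage of the region. The shares 0.1, 0.2, 0.3 and 0.4 appear only as the final multiplier, never as a divisor before banding. SAP 6.1 does not fill the gap: it points to a BSA description further on that the SAP does not contain.

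A programmer who took 10.5 alone and banded the raw entry would compress the scale. Eligible subjects could fail PASI of at least 12, and shrinkage of plaque area would be under-credited in the efficacy endpoint. Endpoint scores could be recomputed later, but subjects wrongly screened out could not be recovered. With about 10 subjects, one reclassified responder is 1/10, or 10 percentage points.

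**Working it through.** **Inputs** (Protocol 10.4 and 10.5): region shares w = 0.1, 0.2, 0.3, 0.4; sign sum S per region, maximum 3 × 4 = 12; Area Score A from 0 to 6; PASI = sum over regions of S × A × w. Regions are listed as head/upper limbs/trunk/lower limbs.

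**Two readings.** *Converted*: regional % = absolute % ÷ w, then band. *Direct*: band the absolute % itself.

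**1. The plan's own maximum.** With the whole body involved, the absolute values are 10/20/30/40%.
- Converted: 100% in every region, A = 6/6/6/6, PASI = 12 × 6 × 1.0 = **72**, as stated.
- Direct: A = 2/2/3/3, PASI = 12 × (0.2 + 0.4 + 0.9 + 1.2) = 12 × 2.7 = **32.4**. Area Scores 4 to 6 can never occur.

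Only conversion reproduces the stated figure and uses the whole band table.

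**2. What direct banding would do at entry.** Assumed subject: 2/3/5/6%, all signs 3, so S = 9.
- Converted: 20/15/16.7/15%, A = 2 throughout, PASI = 9 × 2 × 1.0 = 18.0.
- Direct: A = 1 throughout, PASI = 9 × 1 × 1.0 = 9.0.

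Multiplying the areas by 0.8 or 1.2 changes neither result.

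**3. What it would do to response.** Assumed baseline 4/8/12/16% with S = 9; Week 12 0/1/2/3% with S = 6.
- Converted baseline: 40% in each region, A = 3, PASI = 27.0. Week 12: A = 0/1/1/1, PASI = 6 × 0.9 = 5.4. Change = 5.4/27.0 − 1 = −80.0%.
- Direct baseline: A = 1/1/2/2, PASI = 9 × 1.7 = 15.3. Week 12 is the same 5.4. Change = 5.4/15.3 − 1 = −64.7%, so PASI-75 is missed.

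**4. Near the BSA threshold.** Over all one-decimal allocations with total BSA from 8.0 to 9.9%, direct PASI cannot exceed 12 × 1.0 = 12.0. Converted PASI can reach 22.8 (contiguous bands) or 24.0 (rounding to whole percent). Those are best cases, and for other subjects the readings agree:
- 0.8/1.6/2.4/3.2% (total 8.0) is 8% of every region, so A = 1 either way and the ceiling is 12.0 on both readings.
- 0.9/1.0/2.8/3.7% (total 8.4) converts to 9/5/9.3/9.25%, so A = 1 throughout; with S = 9 both readings give 9.0.

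PASI of at least 12 is therefore hard to reach near 8% BSA for evenly spread disease on either reading.

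**5. Decimals between whole-number bands.** After conversion, some one-decimal entries fall between bands, such as 9.5%. Of the 100 + 200 + 300 + 400 = 1,000 possible entries, 0 + 6 + 12 + 18 = 36 do so (an unweighted count, not an error rate). Contiguous bands or ordinary rounding both resolve them, and the two rules differ by at most one Area Score step in a region.

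**The case for a change.** The strongest case for a change is that a derivation behind both an entry criterion and the main efficacy endpoint should not rest on inference. Section 10.5 hands the task to software and names only the whole-body figure. The SAP, which Protocol 17.3.3.1 makes dominant on statistical matters, does not supply the missing line. The remedy would cost one formula, and the harm at screening could not be undone.

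Much of this stands as fact. The conversion is not written in the readable text, SAP 6.1's pointer to a BSA description leads nowhere, and the 32.4 ceiling is correct arithmetic for direct banding.

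What does not stand is the step from there to a defective plan. Section 10.5 says that the entry is used in assigning the score, and never that the entry is itself placed in the bands. The banded variable is defined in 10.4 and repeated in SAP 6.1, and SAP 6.1 holds no competing scale. Direct banding would contradict that definition and the maximum of 72, and it would leave half of the non-zero Area Scores unused. Appendix 3, which 10.4 cites, and the EDC specification are not visible, so their silence cannot be assumed. The irreversible harm needs a programming error for which there is no evidence, in software that Protocol 18.6 requires to be validated.

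**Conclusion.** The concern does not hold as a fault in the plan. Two scales are in use for a reason: whole-body percentages are needed for total BSA, and regional percentages for PASI. The link between them, dividing by 0.1, 0.2, 0.3 or 0.4, follows from shares printed in the same section as the bands. An analyst who applies 10.4 and 10.5 together obtains the stated maximum of 72 and correct scores. Writing the division down would make explicit what the documents already imply and would alter no score, endpoint or eligibility decision.

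The figures of 32.4, 9.0 against 18.0, and −64.7% against −80.0% describe a misreading, not the plan. The subjects in those examples are assumed, and near 8% BSA the two readings can coincide. The whole-number bands and the SAP's stray pointer are clerical.

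This conclusion assumes that the EDC follows the variable defined in 10.4, which the readable documents cannot confirm. Ordinary software validation would show it: the 2/3/5/6% case with all signs 3 returns 18.0 if the conversion is made and 9.0 if it is not. Even in the adverse case, the descriptive efficacy summaries could be recomputed from the regional BSA entries and sign grades, provided both are stored.

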#### **10.6 Patient Global Impression of Change**

The PGIC is a single item measure that assesses the subject's impression of overall change from Baseline in plaque psoriasis signs and symptoms at the time the questionnaire is administered, using a 7-point visual rating scale ranging from 1 (much improved) to 7 (much worse). See Appendix 4.

Please select the response below that best describes the overall change in your psoriasis since you started taking the trial drug.

Grade	Description
1	Much improved
2	Moderately improved
3	A little improved
4	Stayed the same
5	A little worse

Grade	Description
6	Moderately worse
7	Much worse

## 10.7 Safety Evaluations

### 10.7.1 Vital Signs

Vital signs including temperature, systolic and diastolic blood pressure, heart rate, and respiration rate will be measured. Assessments will be made after the subject has rested in a seated position for at least 5 minutes. Height and weight will also be measured at Visit 1/Screening.

### 10.7.2 Physical Examination

Brief physical examinations at Visit 1/Screening and Visit 2/Baseline will include examination of head and neck, dermatologic (except the indication being studied), cardiovascular, respiratory, gastrointestinal (abdomen), and gross motor and gait. Clinically significant abnormalities at Visit 1/Screening and Visit 2/Baseline will be recorded as medical history. A targeted physical examination will be conducted at follow-up visits driven by the subject's signs and symptoms. Any new or worsening clinically significant abnormalities at any post-Baseline visits will be recorded as AEs.

### 10.7.3 Electrocardiogram

12-lead ECGs will be performed after the subject has rested for at least 10 minutes in the supine position.

The investigator must review all the ECG reports in a timely manner. Note: The investigator will initial and date each ECG report to indicate his/her review. The investigator will note, directly on the report, whether or not any abnormal findings are clinically significant. The investigator must complete an appropriate AE form for any new or worsening abnormal test results that are identified as clinically significant after Baseline.

## 11. PHOTOGRAPHY

Photography documentation is not required in ADX-629-PS-001. However, the investigator may elect to photograph the subject to document the effects of treatment, AEs, or other findings during the trial. All photographs taken as part of ADX-629-PS-001 are for informational purposes only and are not to assist in grading or for any other assessment.

Any photographs taken of readily identifiable features (e.g., the face) will be de-identified (i.e., a masking bar over the eyes). In addition, subject identifiers (i.e., codes) will be used to identify photographs to the appropriate subject.

Note: Subjects may decline to have photographs taken during the conduct of the trial. If a subject initially consents to photographs, then declines further photography, the Sponsor may use the photographs taken under consent for the purposes noted above.

## 12. LABORATORY TESTS

### 12.1 Blood Chemistries, Hematology, and Urinalysis

Blood and urine specimens will be collected at every clinic visit for chemistry, hematology, and urinalysis. At Visit 1/Screening, serology will be performed for HIV, hepatitis B, and hepatitis C (i.e., HepB-sAg and Hep C-Ab) in all subjects and FSH levels will be evaluated in all females. The post-menopausal range for FSH will be based on the central laboratory's range [typically  $\geq 40$  IU/L]. Subjects must be fasting (approximately 8 hours) for Visit 1/Screening and, if possible, for all post-Screening visits. If fasting samples cannot be collected at the time of other Visit 1/Screening procedures, the subject may return to the clinic for sample collection such that the results of the clinical laboratory tests are available for review prior to Visit 2/Baseline; such testing will still be considered "Visit 1/Screening" labs. If a subject arrives at the clinic for any post-Screening visit without fasting for at least 8 hours, laboratory specimens may be collected as non-fasting, at the discretion of the investigator, and with the appropriate fasting status documented on the lab requisition form.

The following laboratory tests will be performed:

LABORATORY TESTS		
Chemistries	Hematology	Urinalysis
Albumin	Hemoglobin	Color
Alkaline phosphatase	Hematocrit	Appearance/Clarity
ALT (SGPT)	MCV	Albumin
AST (SGOT)	MCH	Creatinine
Bilirubin, total	MCHC	Bilirubin
Calcium	RBC (Erythrocytes)	Blood
Carbon Dioxide §	WBC (Leucocytes)	Glucose
Chloride	RDW	Ketones
Creatinine	Differential count	Leukocyte Esterase
GGT	Basophils	Nitrite
Glucose (fasting)	Eosinophils	pH

LABORATORY TESTS		
Chemistries	Hematology	Urinalysis
LDH	Lymphocytes	Protein
Phosphate	Monocytes	Specific gravity
Potassium	Neutrophils	Urobilinogen
Protein, total	Platelets	Microscopic analysis (if needed)
Sodium		Microalbumin/Creatinine Ratio*
Urea (BUN)		
Uric acid		
eGFR*		
Lipid Panel		
Cholesterol, total		
HDL		
Direct LDL		
Triglycerides		

§ Bicarbonate may be substituted if the participating lab does not perform assay for carbon dioxide.

\* If eGFR and/or urine albumin lab assessments are close to, but outside of the limits specified in inclusion #7 and the lab results are deemed not to be clinically significant by the Investigator, the Investigator may request a review by the Medical Monitor of the lab finding(s) in writing to determine the subject's eligibility. The Medical Monitor will review the subject's medical history and concomitant medications in conjunction with the lab results. If the Medical Monitor concurs with the Investigator's assessment of the lab results and assuming that the subject is otherwise qualified to participate, the subject may be enrolled in the study upon receipt of a written approval of the Medical Monitor prior to enrollment.

Sample collection, handling, labeling, and shipping should be done following the instructions provided by the relevant certified laboratory in their lab manual (or equivalent document) and the applicable local regulations.

The investigator must review all the subject's laboratory reports in a timely manner. **NOTE:** The investigator will initial and date each laboratory report to indicate his/her review. The investigator will note, directly on the laboratory report, whether or not any abnormal test results are clinically significant or not clinically significant. Clinical significant laboratory abnormalities that are present at Screening and/or Baseline must be documented in the subject's medical history. In addition, the investigator must complete an appropriate AE form for any new or worsening abnormal test results that are identified as clinically significant after Baseline.

AEs that may be associated with venipuncture and that must be included in the informed consent include:

- Pain
- Bruising
- Bleeding at the puncture site
- Fainting
- Inflammation of the vein

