Although PK variability was observed, a linear correlation was evident in  $C_{max}$  and AUC as dose increased. The half-life ( $t_{1/2}$ ) was consistent across cohorts and days, with mean values in multiple day exposures ranging between 3.49 to 6.83 hours, supportive of BID administration. Little to no accumulation of the drug was seen across all cohorts. At the top dose (600 mg BID), a  $C_{max}$  of 1920 ng/mL (approximately 9.5  $\mu$ M) was consistent with an adequate molar ratio to achieve stoichiometric efficacy against elevated RASP in psoriasis, as described above. Importantly, MDA levels in drug-treated subjects were statistically lower than those of placebo-treated subjects, and inflammation following ingestion of a fatty meal at Day 10, as assessed by lipid profiling, was statistically lower in the drug group relative to the placebo group.

In summary, mechanistic, preclinical, and clinical data suggest that administration of the RASP inhibitor ADX-629 to subjects with plaque psoriasis may sufficiently mitigate the inflammatory response to modify levels of inflammatory mediators and reduce clinical severity.

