### 9.2 Visit 2 (Day 1): Baseline

*Prior to this visit, the investigator or designee will:*

- Review laboratory results to determine if subject is eligible to enroll in the trial.

*At this visit, the investigator or designee will:*

- Query the subject for any changes in health status since the previous visit, including concomitant medications and concurrent procedures/therapies, and document the findings.
- Confirm I/E criteria.
- Review and update medical history, if needed.
- Measure vital signs (see Section 10.7.1).
- Perform clinical evaluations (IGA first, then BSA and PASI). See Section 10.3, Section 10.5, and Section 10.4, respectively.
- Perform a brief physical exam (see Section 10.7.2). Record any findings in medical history.
- Perform ECG (see Section 10.7.3).
- Collect blood for baseline blood biomarker analysis (RASP ELISAs and cytokines) prior to first test article administration (see Section 12.3).
- Collect blood and urine samples for clinical laboratory tests (chemistry, hematology, and urinalysis). If possible, subjects should be fasting for approximately 8 hours.
- Perform a UPT for all WOCBP. The result must be negative for the subject to be enrolled in the trial.
- Identify a lesion area for skin sampling (this location will be used for all subsequent assessments during the study). Collect non-invasive skin samples from lesional and non-lesional (perilesional to the lesional sample) skin (see Section 12.2).  
**Note:** Be sure to capture and document location of collection for future collections.
- Dispense Subject Instruction Sheet.
- Document Test Article Accountability and dispense the test article.
- Supervise the first dose of test article in the clinic.
- Document any AEs.
- Schedule the next visit.

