**SCHEDE OF EVENTS**

## 5. DEFINITIONS

- Study Day: The study day is the day of study relative to the date of test article application (Baseline visit / Day 1). Study Day = follow-up visit date – first dose date +1.

- Baseline: The baseline assessment is defined as the last non-missing measurement collected at the Baseline visit (Visit 2) prior to test article application.

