#### ***8.8.7 Clinical Laboratory Tests***

All laboratory data (chemistry, hematology, urinalysis, and serology) will be summarized and listed in the units received by the laboratory at each study visit. Shift tables will be presented to facilitate the evaluation of change from Baseline to Week 4, 8, and 12 /EOT. Results outside of normal limits will be classified as clinically significant or not clinically significant. Clinically significant laboratory results may or may not have been coded as AEs, at the discretion of the Investigator.

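### Glucose and lipid summaries and shift tables can mix fasted and fed samples, because fasting is compulsory only at Screening and the SAP does not use the recorded fasting status

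*Protocol*

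**What the plan says.** The chemistry list in Protocol Section 12.1 marks glucose as a fasting test and adds a lipid panel of total cholesterol, HDL, direct LDL and triglycerides. On fasting, the section states: "Subjects must be fasting (approximately 8 hours) for Visit 1/Screening and, if possible, for all post-Screening visits". If a subject arrives unfasted at a later visit, "laboratory specimens may be collected as non-fasting, at the discretion of the investigator", "with the appropriate fasting status documented on the lab requisition form".

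The visit procedures agree. Section 9.2 (Visit 2/Baseline) says "If possible, subjects should be fasting for approximately 8 hours", and Sections 9.4 to 9.6 make the same request for Visits 4, 5 and 6.

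SAP Section 5 defines Baseline as "the last non-missing measurement collected at the Baseline visit (Visit 2) prior to test article application". SAP Section 8.8.7 summarises and lists all laboratory data by visit and adds: "Shift tables will be presented to facilitate the evaluation of change from Baseline to Week 4, 8, and 12 /EOT". It contains no split, flag or restriction by fasting status. Protocol Section 17.3.1.5, which builds the shift tables by analyte and out-of-range flag, has none either. SAP Section 7.5 repeats the opening of Protocol Section 12.1 but leaves out the fasting sentences.

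**The concern.** Change from Baseline in laboratory tests is a named safety endpoint (Protocol Section 17.2.1, SAP Section 3.3), and the sample-size statement calls this primarily a safety and tolerability trial. Glucose and triglycerides respond to recent food. If a subject is fed at Visit 2 and fasted later, or the reverse, part of the difference comes from the meal. There is a single open-label arm, so no concurrent control would show the same meal effect and reveal it. With about 10 subjects, one mismatched subject is 10% of a shift table.

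The only sample that must be fasting, Screening, is not the reference for change. The item needed to separate the two situations is recorded on the requisition but has no stated role in the analysis.

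**Working it through.** The plan gives no figure to reproduce: N=10 is stated without a calculation, and no fasting rate or meal effect appears. The check is a comparison of the sections, followed by an illustration of how often mismatched pairs could arise.

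**Comparison**

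| Step | Place | Fasting |
|---|---|---|
| Screening sample | Protocol 12.1, 9.1 | Compulsory |
| Visit 2 sample, the reference value | Protocol 9.2, SAP 5 | Requested where possible |
| Visits 4, 5 and 6, the comparison values | Protocol 9.4 to 9.6 | Requested where possible |
| Record of status | Protocol 12.1 | On the requisition form |
| Summaries and shift tables | SAP 8.8.7, Protocol 17.3.1.5 | Not mentioned |

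Both ends of every Baseline-to-visit pair may therefore be fasted or fed, and the tables as specified do not distinguish them. That the SAP pools all values is inferred from its reference to all laboratory data and its silence on fasting. It does not say so expressly.

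**Illustration**

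Assumption: each subject is fasting at each visit with probability p, independently across visits and subjects. The documents give no value for p, so a range is shown, with 10 subjects throughout.

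- Probability that a pair differs in status: d = 2p(1−p)
- Expected mismatched pairs per post-Baseline visit: 10d
- Chance of at least one at a visit: 1 − (1−d)^10
- Expected mismatched pairs over three post-Baseline visits: 30d
- Expected pairs fasting at both visits: 10p²

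| p | d | 10d | At least one | 30d | 10p² |
|---|---|---|---|---|---|
| 0.95 | 0.095 | 0.95 | 63% | 2.9 | 9.0 |
| 0.90 | 0.18 | 1.8 | 86% | 5.4 | 8.1 |
| 0.80 | 0.32 | 3.2 | 98% | 9.6 | 6.4 |
| 0.50 | 0.50 | 5.0 | >99% | 15.0 | 2.5 |

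Worked line for p = 0.90: d = 2 × 0.90 × 0.10 = 0.18; 10 × 0.18 = 1.8; 1 − 0.82^10 = 0.863; 30 × 0.18 = 5.4; 10 × 0.81 = 8.1.

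Under this model, half the mismatches run from fasted to fed and half from fed to fasted. It therefore shows how often pairs could be contaminated, not a net direction. A mismatched pair changes a shift-table cell only if the meal moves the value across a range limit.

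**The case against.** Much of the case against is sound. Fasting is requested at every post-Screening visit, so a non-fasting draw is an exception made at the investigator's discretion and documented. The investigator judges clinical significance on each report and may discount a fed value. All results are also listed by subject. The tables are descriptive and no formal test depends on them. No stopping rule in Protocol Section 14.3 names glucose or a lipid, and the general laboratory rule there acts on individual results that must be repeated for confirmation. The eCRF, laboratory manual, Schedule of Events and subject instruction sheet are not shown and could hold further fasting instructions or an analysis flag. These points limit the seriousness, but none makes the tables use fasting status.

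Four stronger readings are tempting and are not supported:

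- **A stated percentage bias in triglycerides.** This needs a fed-to-fasted ratio and a count of subjects fed at Baseline, neither of which is in the documents. SAP 8.8.7 also specifies no mean change for laboratory tests, unlike SAP 8.8.5 for vital signs and 8.8.6 for ECG.
- **A known direction, with Baseline fed and later visits fasted.** An evening Day 1 visit is only a possibility in Protocol Section 6.2, and nothing shown says whether the morning dose is taken with food.
- **The Phase 1 result as proof that the drug alters these readings.** Protocol Section 1 says "inflammation following ingestion of a fatty meal at Day 10, as assessed by lipid profiling, was statistically lower" in the drug group. That concerns inflammation after a meal. It does not say that the clinical lipid panel changes.
- **False clinically significant flags.** These would require the investigator to ignore the recorded status. Which reference range applies to non-fasting samples is not shown.

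**Conclusion.** The point holds as a modest one. Followed as written, the plan mixes fasted and possibly fed values in the glucose and lipid summaries and shift tables, against a Visit 2 Baseline that need not be fasting. It matters mainly for glucose and triglycerides, less for total cholesterol, HDL and direct LDL, and not for the rest of the laboratory endpoint. With one arm of about 10 subjects, those tables cannot separate a meal effect from a drug effect.

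The size and direction of any distortion are unknown from the documents. The mismatch counts above rest on an assumed fasting rate and on independence between visits. They show that even good compliance could leave some mismatched pairs, not that the results will be misleading.

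**What to change.** Carry the fasting status from the requisition into the analysis data, first confirming that it reaches the eCRF or the laboratory transfer. In SAP Section 8.8.7, for glucose and the four lipid analytes:

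- keep the all-values by-visit summaries and shift tables;
- beside them, present the same tables for subjects fasting at both Visit 2 and the post-Baseline visit concerned, with n shown;
- flag non-fasting values, and values with unknown status, in the subject listing.

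Do not replace a non-fasting Visit 2 value with the Screening value. That would mix two baselines and depart from SAP Section 5. Screening can also fall up to 21 days before Baseline and precede washout of prohibited medication (Protocol Synopsis, Visit 1), so a washout effect could take the place of the meal effect.

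The cost is one SAP paragraph, one data item and a few extra tables for five analytes. The fasting-pair tables will have a smaller n: under the assumptions above, about 8.1 of 10 at p = 0.90 and 6.4 at p = 0.80. No safety data are removed, and no visit or treatment procedure changes.
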